8.2.7 Eastern Cooperative Oncology Group Performance Scale

The investigator or qualified designee will assess ECOG status (Appendix 9), prior to the administration of study intervention on Day 1 of each cycle at the timepoints identified in the SoA.

8.3 Safety Assessments

Details regarding specific safety procedures/assessments to be performed in this study are provided. The total amount of blood/tissue to be drawn/collected over the course of the study (from prestudy to poststudy visits), including approximate blood/tissue volumes drawn/collected by visit and by sample type per participant, can be found in the Procedures Manual.

Planned time points for all safety assessments are provided in the SoA.

8.3.1 Physical Examinations

Physical examinations (full or directed) will be conducted by an investigator or medically qualified designee (consistent with local requirements) as per institutional standard. The time points for full physical examinations are described in Section 1.3.

Investigators should pay special attention to clinical signs related to previous serious illnesses.

8.3.1.1 Full Physical Examination

The investigator or qualified designee will perform a complete physical examination during the screening period. Height and weight will also be measured and recorded. Clinically significant abnormal findings should be recorded as medical history. After the first dose of study intervention, new clinically significant abnormal findings should be recorded as AEs.

8.3.1.2 Directed Physical Examination

For cycles that do not required a full physical examination as defined in Section 1.3, the investigator or qualified designee will perform a directed physical examination as clinically indicated prior to study intervention administration. Weight will also be measured and recorded. New clinically significant abnormal findings should be recorded as AEs.

8.3.2 Vital Signs

The investigator or qualified designee will take vital signs at screening, prior to the administration of each dose of study intervention and during the follow-up period as specified in the SoA. Vital signs include heart rate, respiratory rate, O₂ saturation, blood pressure, and temperature.

8.3.3 Electrocardiograms

A standard 12-lead ECG will be performed using local standard procedures. The timing of ECGs is specified in the SoA. Clinically significant abnormal findings should be recorded as medical history. Additional ECGs may be performed as clinically necessary.

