6.2.2 Timing of Study Interventions

Treatment cycles for this study are 21 days each cycle. All study interventions will begin after all predose study procedures and assessments have been completed, as detailed in Section 1.3. Every effort should be made to begin the first dose of study intervention on the day of randomization; however, if this is not achieved, study intervention is to be initiated no later than 3 days from the date of randomization. All subsequent cycles of study intervention may be administered up to 3 days before or 3 days after the scheduled day due to administrative reasons per the investigator's judgment.

The reason for any variability in the administration of the study intervention(s) outside of the protocol-specified windows is to be documented in the participant's chart and recorded in the eCRFs.

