8.3.4 Clinical Safety Laboratory Assessments

Refer to Appendix 2 for the list of clinical laboratory tests to be performed and to the SoA for the timing and frequency.

- The investigator or medically qualified designee (consistent with local requirements) must review the laboratory report, document this review, and record any clinically relevant changes occurring during the study in the AE section of the CRF. The laboratory reports must be filed with the source documents. Clinically significant abnormal laboratory findings are those which are not associated with the underlying disease, unless judged by the investigator to be more severe than expected for the participant's condition.
- All protocol-required laboratory assessments, as defined in Appendix 2, must be conducted in accordance with the Procedures Manual and the SoA.
- If laboratory values from nonprotocol-specified laboratory assessments performed at the institution's local laboratory require a change in study participant management or are considered clinically significant by the investigator (eg, SAE or AE or dose modification), then the results must be recorded in the appropriate CRF (eg, SLAB).
- For any laboratory tests with values considered clinically significantly abnormal during participation in the study or within 30 days after the last dose of study intervention, every attempt should be made to perform repeat assessments until the values return to normal or baseline or if a new baseline is established as determined by the investigator.

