8.4 Adverse Events, Serious Adverse Events, and Other Reportable Safety Events

The definitions of an AE or SAE, as well as the method of recording, evaluating, and assessing causality of AE and SAE and the procedures for completing and transmitting AE, SAE, and other reportable safety event reports can be found in Appendix 3.

AEs, SAEs, and other reportable safety events will be reported by the participant (or, when appropriate, by a caregiver, surrogate, or the participant's legally authorized representative).

The investigator and any designees are responsible for detecting, documenting, and reporting events that meet the definition of an AE or SAE as well as other reportable safety events. Investigators remain responsible for following up AEs, SAEs, and other reportable safety events for outcome according to Section 8.4.3.

The investigator, who is a qualified physician, will assess events that meet the definition of an AE or SAE as well as other reportable safety events with respect to seriousness, intensity/toxicity and causality.

8.4.1 Time Period and Frequency for Collecting AE, SAE, and Other Reportable Safety Event Information

All AEs, SAEs, and other reportable safety events that occur after the consent form is signed but before intervention randomization must be reported by the investigator if the participant is receiving placebo run-in or other run-in treatment, if the event cause the participant to be excluded from the study, or is the result of a protocol-specified intervention, including but not limited to washout or discontinuation of usual therapy, diet, or a procedure.

- All AEs from the time of intervention randomization through 30 days following cessation of study intervention must be reported by the investigator.
- All AEs meeting serious criteria, from the time of intervention randomization through 90 days following cessation of study intervention or 30 days following cessation of study intervention if the participant initiates new anticancer therapy, whichever is earlier, must be reported by the investigator.

- All pregnancies and exposure during breastfeeding, from the time of intervention randomization through 120 days following cessation of study intervention, or 30 days following cessation of study intervention if the participant initiates new anticancer therapy must be reported by the investigator.

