10.3.1 Definition of AE

AE definition

- An AE is any untoward medical occurrence in a clinical study participant, temporally associated with the use of study intervention, whether or not considered related to the study intervention.
- NOTE: An AE can therefore be any unfavorable and unintended sign (including an abnormal laboratory finding), symptom, or disease (new or exacerbated) temporally associated with the use of a study intervention.
- NOTE: For purposes of AE definition, study intervention (also referred to as Sponsor's product) includes any pharmaceutical product, biological product, vaccine, diagnostic agent, or protocol-specified procedure whether investigational or marketed (including placebo, active comparator product, or run-in intervention), manufactured by, licensed by, provided by, or distributed by the Sponsor for human use in this study.

Events meeting the AE definition

- Any abnormal laboratory test results (hematology, clinical chemistry, or urinalysis) or other safety assessments (eg, ECG, radiological scans, vital signs measurements), including those that worsen from baseline, considered clinically significant in the medical and scientific judgment of the investigator.
- Exacerbation of a chronic or intermittent pre-existing condition including either an increase in frequency and/or intensity of the condition.
- New conditions detected or diagnosed after study intervention administration even though it may have been present before the start of the study.
- Signs, symptoms, or the clinical sequelae of a suspected drug-drug interaction.
- Signs, symptoms, or the clinical sequelae of a suspected overdose of either study intervention or a concomitant medication.
- For all reports of overdose (whether accidental or intentional) with an associated AE, the AE term should reflect the clinical symptoms or abnormal test result. An overdose without any associated clinical symptoms or abnormal laboratory results is reported using the terminology "accidental or intentional overdose without adverse effect."

Events NOT meeting the AE definition

- Medical or surgical procedure (eg, endoscopy, appendectomy): the condition that leads to the procedure is the AE.
- Situations in which an untoward medical occurrence did not occur (social and/or convenience admission to a hospital).
- Anticipated day-to-day fluctuations of pre-existing disease(s) or condition(s) present or detected at the start of the study that do not worsen.

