10.3.2 Definition of SAE

If an event is not an AE per definition above, then it cannot be an SAE even if serious conditions are met.

An SAE is defined as any untoward medical occurrence that, at any dose:

1. Results in death

2. Is life-threatening

- The term “life-threatening” in the definition of “serious” refers to an event in which the participant was at risk of death at the time of the event. It does not refer to an event, which hypothetically might have caused death, if it were more severe.

3. Requires inpatient hospitalization or prolongation of existing hospitalization

- Hospitalization is defined as an inpatient admission, regardless of length of stay, even if the hospitalization is a precautionary measure for continued observation. (Note: Hospitalization for an elective procedure to treat a pre-existing condition that has not worsened is not an SAE.) A pre-existing condition is a clinical condition that is diagnosed prior to the use of an MSD product and is documented in the participant’s medical history.

4. Results in persistent or significant disability/incapacity

- The term disability means a substantial disruption of a person’s ability to conduct normal life functions.
- This definition is not intended to include experiences of relatively minor medical significance such as uncomplicated headache, nausea, vomiting, diarrhea, influenza,

and accidental trauma (eg, sprained ankle) that may interfere with or prevent everyday life functions but do not constitute a substantial disruption.

5. Is a congenital anomaly/birth defect

- In offspring of participant taking the product regardless of time to diagnosis.

6. Other important medical events

- Medical or scientific judgment should be exercised in deciding whether SAE reporting is appropriate in other situations such as important medical events that may not be immediately life-threatening or result in death or hospitalization but may jeopardize the participant or may require medical or surgical intervention to prevent 1 of the other outcomes listed in the above definition. These events should usually be considered serious.

Examples of such events include invasive or malignant cancers, intensive treatment in an emergency room or at home for allergic bronchospasm, blood dyscrasias or convulsions that do not result in hospitalization, or development of drug dependency or drug abuse.

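### Section 8.3.3 files every clinically significant ECG finding as medical history, including on-treatment findings that Appendix 3 makes adverse events

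*Combined protocol and SAP*

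**What the plan says.** Section 8.3.3 defers ECG timing to the schedule of activities, allows additional ECGs when clinically needed, and gives one recording instruction: "Clinically significant abnormal findings should be recorded as medical history". It does not mention AEs.

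The schedules in Section 1.3 place a 12-lead ECG at screening and again at Cycle 3 Day 1 in Arm 1 and in Arm 2.

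Appendix 3, Section 10.3.1, lists among the events that meet the AE definition abnormal laboratory results and results of "other safety assessments (eg, ECG, radiological scans, vital signs measurements), including those that worsen from baseline", when the investigator judges them clinically significant. Section 8.4.1 then states: "All AEs from the time of intervention randomization through 30 days following cessation of study intervention must be reported by the investigator".

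The neighbouring parts of Section 8.3 treat on-study findings as AEs:

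- Full physical examination (8.3.1.1): the same medical-history sentence as 8.3.3, followed by "After the first dose of study intervention, new clinically significant abnormal findings should be recorded as AEs".
- Directed physical examination (8.3.1.2): "New clinically significant abnormal findings should be recorded as AEs".
- Laboratory tests (8.3.4): the investigator must "record any clinically relevant changes occurring during the study in the AE section of the CRF".

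**The concern.** Read literally, 8.3.3 sends a clinically significant abnormality first seen on the Cycle 3 ECG, or on an unscheduled on-treatment ECG, to medical history. Medical history describes the participant before treatment, so a treatment-emergent finding filed there would look like a baseline condition.

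AEs are a secondary endpoint, and AE terms feed the tiered between-arm safety comparison in Section 9.6.2. If some sites follow 8.3.3 and others follow Appendix 3, the same finding is an AE at one site and baseline history at another. AE counts would then partly reflect which page the site staff consulted.

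**Working it through.** The documents state no figure on this point, so the check sets the passages side by side.

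**1. Which ECGs does 8.3.3 govern?** All of them: the section refers to the schedule for timing and adds unscheduled ECGs. Scheduled ECGs per participant = 1 (screening) + 1 (Cycle 3 Day 1) = 2, in each arm.

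**2. What does each instruction require?**

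| ECG | Under 8.3.3 | Under 10.3.1 with 8.4.1 |
|---|---|---|
| Screening | Medical history | Before randomization; reportable only in the circumstances 8.4.1 lists. No general conflict |
| Cycle 3 Day 1, new or worsened finding | Medical history | AE, to be reported |
| Unscheduled, after randomization, new or worsened finding | Medical history | AE, to be reported |

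The direct conflict is with 10.3.1, which names ECG. Section 8.4.1 does not mention ECG; it conflicts because it requires every AE in its window to be reported.

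**3. Does an exception remove the conflict?** Section 10.3.1 refers to 8.4.6 for protocol-specific exceptions, and 8.4.6 excepts only progression of the cancer under study. ECG findings are not excepted.

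**4. Does medical history fit an on-treatment finding?** No. Section 10.3.2 says: "A pre-existing condition is a clinical condition that is diagnosed prior to the use of an MSD product", and adds that such a condition is documented in the medical history. A finding that first appears at Cycle 3 does not qualify.

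**5. How do the other Section 8.3 rules compare?** Four assessments carry a recording rule: 8.3.1.1, 8.3.1.2, 8.3.3 and 8.3.4. Vital signs (8.3.2) carry none. Three of the four send on-study findings to AEs; 8.3.3 is the exception. It matches the first half of the two-part rule in 8.3.1.1 and lacks the second, which suggests a dropped sentence.

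**6. How many assessments are exposed?** One scheduled on-treatment ECG for each participant who reaches Cycle 3. With approximately 200 randomized, that is at most about 200 × 1 = 200, and fewer after early discontinuation, plus any unscheduled ECGs. No rate of clinically significant findings is given, so the number of affected records cannot be computed.

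**7. When should the AE rule start?** Section 8.4.1 starts at randomization and 8.3.1.1 at first dose. Section 6.2.2 says that if dosing does not begin on the day of randomization, "study intervention is to be initiated no later than 3 days from the date of randomization". The two starting points can therefore differ by 0 to 3 days.

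**The case against.** The strongest reply is that the intended meaning can be recovered. Section 8.4 sends the reader to Appendix 3 for AE definitions and recording, and Appendix 3 names ECG. The schedules list medical history at screening only; the treatment schedules have AE monitoring but no medical-history row. Section 8.1.4 describes medical history as active conditions and clinically significant ones from the previous 10 years. Section 8.3.3 does not say that ECG findings are exempt from AE reporting, so a site could satisfy every section. Vital signs have no recording rule at all and rely on Appendix 3 without difficulty. The consequence is also small: ECG changes from baseline are summarised by arm as Tier 3 in Table 14, and Section 9.6.2 separately mentions events in ECG parameters.

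Much of this stands. It supports screening as the intent and keeps the severity low. It does not remove the problem. Silence, as for vital signs, leaves Appendix 3 to operate; 8.3.3 instead states a destination, and for the Cycle 3 ECG it is the wrong one under the protocol's own AE definition. Section 8.3.3 is the section written specifically for ECGs, and it does not point to Appendix 3.

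**Conclusion.** The concern holds: 8.3.3 as written contradicts 10.3.1, and through it 8.4.1, for any post-randomization ECG with a new or worsened clinically significant finding. It is a wording fault of low severity that should be corrected.

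The possible effect is confined to AE counts. The findings would not necessarily be lost, because 10.3.1 and 8.4.1 still require them to be reported; the risk is inconsistent filing between sites. No efficacy analysis is touched. The size of the effect is unknown, since it depends on how often such findings occur and how many sites rely on 8.3.3 alone, and the documents inform neither. The conclusion rests on the text only and needs no numerical assumption.

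**What to change.** In Section 8.3.3, limit the medical-history sentence to the screening ECG. Add that new or worsened clinically significant ECG findings after that are recorded as AEs under 10.3.1, using the reporting periods of 8.4.1, with routine AE reporting from randomization. Referring to 8.4.1 as a whole also keeps its narrower rule for events between consent and randomization.

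Do not carry over the first-dose starting point from 8.3.1.1, because it can fall up to 3 days after the 8.4.1 window opens.

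The cost is one or two sentences, with no new procedure, visit or data field.

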8.3.4 Clinical Safety Laboratory Assessments

Refer to Appendix 2 for the list of clinical laboratory tests to be performed and to the SoA for the timing and frequency.

- The investigator or medically qualified designee (consistent with local requirements) must review the laboratory report, document this review, and record any clinically relevant changes occurring during the study in the AE section of the CRF. The laboratory reports must be filed with the source documents. Clinically significant abnormal laboratory findings are those which are not associated with the underlying disease, unless judged by the investigator to be more severe than expected for the participant's condition.
- All protocol-required laboratory assessments, as defined in Appendix 2, must be conducted in accordance with the Procedures Manual and the SoA.
- If laboratory values from nonprotocol-specified laboratory assessments performed at the institution's local laboratory require a change in study participant management or are considered clinically significant by the investigator (eg, SAE or AE or dose modification), then the results must be recorded in the appropriate CRF (eg, SLAB).
- For any laboratory tests with values considered clinically significantly abnormal during participation in the study or within 30 days after the last dose of study intervention, every attempt should be made to perform repeat assessments until the values return to normal or baseline or if a new baseline is established as determined by the investigator.

8.3.4.1 Laboratory Safety Evaluations (Hematology, Chemistry, and Urinalysis)

Laboratory tests for hematology, chemistry, and urinalysis are specified in Appendix 2.

Laboratory tests for screening should be performed within 7 days prior to the first dose of study intervention. An exception is hepatitis and thyroid serologies, which may be performed within 28 days prior to first dose. After Cycle 1, predose laboratory safety tests can be conducted up to 72 hours prior to dosing unless otherwise noted on the flow charts.

Laboratory test results must be reviewed by the investigator or qualified designee and found to be acceptable prior to administration of each dose of study intervention. Unresolved abnormal laboratory values that are drug-related AEs should be followed until resolution. Laboratory tests do not need to be repeated after the EOT if laboratory results are within normal range.

8.3.4.2 Pregnancy Test

All women who are being considered for participation in the study, and who are not surgically sterilized or postmenopausal, must be tested for pregnancy within 24 hours of the first dose of study medication on C1D1 and 30 days posttreatment. Additional pregnancy testing can be conducted if required by local regulations or if clinically indicated. If a urine test is positive or not evaluable, a serum test will be required. Participants must be excluded/discontinued from the study in the event of a positive or borderline-positive test result. Refer to Appendix 7 for country-specific requirements.

8.4 Adverse Events, Serious Adverse Events, and Other Reportable Safety Events

The definitions of an AE or SAE, as well as the method of recording, evaluating, and assessing causality of AE and SAE and the procedures for completing and transmitting AE, SAE, and other reportable safety event reports can be found in Appendix 3.

AEs, SAEs, and other reportable safety events will be reported by the participant (or, when appropriate, by a caregiver, surrogate, or the participant's legally authorized representative).

The investigator and any designees are responsible for detecting, documenting, and reporting events that meet the definition of an AE or SAE as well as other reportable safety events. Investigators remain responsible for following up AEs, SAEs, and other reportable safety events for outcome according to Section 8.4.3.

The investigator, who is a qualified physician, will assess events that meet the definition of an AE or SAE as well as other reportable safety events with respect to seriousness, intensity/toxicity and causality.

8.4.1 Time Period and Frequency for Collecting AE, SAE, and Other Reportable Safety Event Information

All AEs, SAEs, and other reportable safety events that occur after the consent form is signed but before intervention randomization must be reported by the investigator if the participant is receiving placebo run-in or other run-in treatment, if the event cause the participant to be excluded from the study, or is the result of a protocol-specified intervention, including but not limited to washout or discontinuation of usual therapy, diet, or a procedure.

- All AEs from the time of intervention randomization through 30 days following cessation of study intervention must be reported by the investigator.
- All AEs meeting serious criteria, from the time of intervention randomization through 90 days following cessation of study intervention or 30 days following cessation of study intervention if the participant initiates new anticancer therapy, whichever is earlier, must be reported by the investigator.

- All pregnancies and exposure during breastfeeding, from the time of intervention randomization through 120 days following cessation of study intervention, or 30 days following cessation of study intervention if the participant initiates new anticancer therapy must be reported by the investigator.
- Additionally, any SAE brought to the attention of an investigator at any time outside of the time period specified above must be reported immediately to the Sponsor if the event is considered related to study intervention.

Investigators are not obligated to actively seek AEs or SAEs or other reportable safety events in former study participants. However, if the investigator learns of any SAE, including a death, at any time after a participant has been discharged from the study, and he/she considers the event to be reasonably related to the study intervention or study participation, the investigator must promptly notify the Sponsor.

All initial and follow-up AEs, SAEs, and other reportable safety events will be recorded and reported to the Sponsor or designee within the time frames as indicated in [Table 10](#).

Table 10 Reporting Time Periods and Time Frames for Adverse Events and Other Reportable Safety Events

Type of Event	Reporting Time Period: Consent to Randomization/ Allocation	Reporting Time Period: Randomization/ Allocation through Protocol-specified Follow-up Period	Reporting Time Period: After the Protocol- specified Follow-up Period	Time Frame to Report Event and Follow-up Information to Sponsor:
Nonserious Adverse Event (NSAE)	Report if: - due to protocol-specified intervention - causes exclusion - participant is receiving placebo run-in or other run-in treatment	Report all	Not required	Per data entry guidelines
Serious Adverse Event (SAE) including Cancer and Overdose	Report if: - due to protocol-specified intervention - causes exclusion - participant is receiving placebo run-in or other run-in treatment	Report all	Report if: - drug/vaccine related. (Follow ongoing to outcome)	Within 24 hours of learning of event
Pregnancy/ Lactation Exposure	Report if: - due to intervention - causes exclusion	Report all	Previously reported – Follow to completion/termination; report outcome	Within 24 hours of learning of event

Type of Event	Reporting Time Period: Consent to Randomization/ Allocation	Reporting Time Period: Randomization/ Allocation through Protocol-specified Follow-up Period	Reporting Time Period: After the Protocol- specified Follow-up Period	Time Frame to Report Event and Follow-up Information to Sponsor:
Event of Clinical Interest (ECI) (require regulatory reporting)	Report if: - due to intervention - causes exclusion	Report - potential drug-induced liver injury (DILI) - require regulatory reporting	Not required	Within 24 hours of learning of event
Event of Clinical Interest (do not require regulatory reporting)	Report if: - due to intervention - causes exclusion	Report - non-DILI ECIs and those not requiring regulatory reporting	Not required	Within 5 calendar days of learning of event

